BIOMEDICAL RESEARCH PROTOCOL UNIVERSITY OF MISSOURI

Project Title: Estrogen receptor alpha signaling in endothelial cells exacerbates arterial

stiffening via upregulation of ENaC in insulin resistant females

IRB Number: 2012990 Version Number: 24

Version Date: October 30, 2023

Principal Investigator: [name]

Funding Source: NHLBI

Clinical Trial Phase: Phase II

Clinicaltrials.gov Number: NCT03837626 Study Drug/Study Device: *Amiloride*

I. Research Objectives/Background

Hypothesis: Estrogen action, through the endothelial cell (EC) estrogen receptor alpha (ERα) upregulates EC ENaC expression and activity exacerbating endothelial and arterial stiffening in overweight and obese, insulin resistant (IR) premenopausal females. The corollary to this hypothesis is that ENaC inhibition will have a greater impact on arterial stiffness in overweight and obese, premenopausal insulin resistant women than in overweight and obese IR postmenopausal women or age matched obese IR men.

To test our hypothesis, we will use in vivo measures of endothelial function and arterial stiffness in a cohort of overweight and obese IR subjects treated with amiloride, an ENaC inhibitor, to accomplish the follow aim:

To determine whether treatment with the ENaC inhibitor, amiloride, improves endothelial function and arterial stiffness in overweight and obese IR subjects in a randomized placebo-controlled trial examining pre and postmenopausal women and age-matched men.

II. Drugs/Biologics/Devices

Following screening, male and female subjects will be randomized to a doubled blinded placebo control trial. Subjects will start on either a 24-week treatment with oral medication, either amiloride, a max dose of 5 mg daily, or placebo intervention.

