- 9. Participation in regular exercise > 3 days/wk per week at a moderate or vigorous intensity
- 10. Pregnancy or lactation in women (or women not using contraceptives)
- 11. Women who plan to become pregnant during the duration of the trial
- 12. Chronic use of NSAIDs
- 13. Potassium level > 5.0 mqE/L at time of screening
- 14. Blood pressure at screening <110/70

VI. Number of Subjects

Men (n=72) and women (n=87) (total=159 overweight/obese subjects) with IR will be recruited for this study. Postmenopausal women are those who have not menstruated for at least **6 months**.^{5,6}

Table 1 presents the estimated sample sizes necessary to test the response to amiloride and compare the

[figure not shown]
Table 1. Repeated- measures design for amiloride treatment	Baseline and treatment cfPWV (m/s)	SD of the Δ	Power	Alph	Calculated sampled size	Final recruitment target 2:1 Amiloride Placebo	
1. Premenopausal women	7.2> 6.2	1.2	90%	0.05	30	34	17
2. Young men (30-50 y)	7.1> 6.6	0.5	90%	0.05	21	24	12
3. Old men (51-70 y)	8.0> 7.5	0.5	90%	0.05	21	24	12
4. Postmenopausal women	8.0> 7.5	0.5	90%	0.05	21	24	12

responses of men and women. We hypothesize that the improvement in carotid femoral pulse wave velocity (cfPWV) in men will be intermediate between the two female groups. Because of the negative effect of estrogen-stimulated ENaC activation, we believe that amiloride will benefit premenopausal women more (a Δ , reduction of 1.0 m/s) than the other groups. Our sample size also allows for a greater variation in the response of premenopausal women due to the effects of reproductive hormones in this group⁷ (SD of the change of 1.2 m/s, **Table 1**). By contrast, we anticipate that the response of post-menopausal women (**Table 1**) will be equal to that of the older men or could even be the lowest of all the groups, given a lesser contribution of estrogen signaling in the activation of ENaC in this population. In summary, the final sample sizes listed below will give 90% power to detect each group's changes in cfPWV.

VII. Study Procedures/Design/Treatment Plan

Planned visits:

Screening visit: Written consent, DOB, gender, ethnic/racial category, height, waist circumference, body weight (history of body weight gain or loss, vital signs, medical history and screening laboratories. Entire visit

is expected to take up to an 1 hour.

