**STATISTICAL ANALYSIS PLAN
UNIVERSITY OF MISSOURI**

Project Title: Estrogen receptor alpha signaling in endothelial cells exacerbates arterial stiffening via upregulation of ENaC in insulin resistant females

IRB Number: 2012990

Version Date: November 13, 2025

Principal Investigator: [name]

Funding Source: **NHLBI**

Clinical Trial Phase: *Phase II*

Clinicaltrials.gov Number: NCT03837626

Study Drug/Study Device: *Amiloride*

Statistical analysis plan – primary outcome

Linear mixed-effects models were used to evaluate changes in continuous outcome variables. Each outcome was analyzed in a separate model using the **lmer** function in the *lme4* package (R Foundation for Statistical Computing). Fixed effects included time, group, and their interaction (time \times group). A random intercept for participant ID was included to account for within-participant correlation from repeated measurements. Models were estimated using restricted maximum likelihood (REML).

Model assumptions were examined and satisfied, including assessment of normality of residuals, homogeneity of variance, multicollinearity, and evaluation for singular fit. Missing data were handled by the default behavior of **lmer()**, which excludes observations containing NA values; no imputation was performed.

Continuous data were visualized using GraphPad Prism (version 10.0) and are presented as mean values with 95% confidence intervals. Because only two groups were compared, no correction for multiple comparisons was applied.

Significance as set as $p \leq 0.05$.

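### Section VI claims 90% power in each group, but amiloride versus placebo at the listed 2:1 sizes has about 79-81% power, or about 73-75% after the attrition Table 1 implies

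*Protocol*

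**What the plan says.** Protocol Section I describes the aim as testing amiloride "in a randomized placebo-controlled trial examining pre and postmenopausal women and age-matched men". Section VI introduces the sample size with "Table 1 presents the estimated sample sizes necessary to test the response to amiloride and compare the" responses of men and women. The title of Table 1 calls it a repeated-"measures design for amiloride treatment".

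For premenopausal women the table assumes a fall in cfPWV from 7.2 to 6.2 m/s, with an SD of the change of 1.2. For young men, old men and postmenopausal women it assumes a fall of 0.5 m/s with an SD of 0.5. Power is 90% and alpha 0.05 throughout. The calculated sizes are 30 and 21. The last columns, headed "Final recruitment target 2:1", give 34 amiloride and 17 placebo for premenopausal women, and 24 and 12 for each other group.

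The section concludes: "In summary, the final sample sizes listed below will give 90% power to detect each" group's change in cfPWV. It does not state the test, the sidedness, the expected placebo change or a dropout allowance.

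The SAP fits a mixed model with time, group and their interaction. It says: "Because only two groups were compared, no correction for multiple comparisons was applied". It describes no sex or menopause stratum.

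**The concern.** The 90% is attached to the final 2:1 sizes, but the calculated column contains one number per group and that number reappears, inflated, only in the amiloride column. If 30 and 21 were sizes per arm for a two-arm comparison, halving the placebo arm must lower the power for that comparison, and the closing sentence would no longer be true of it.

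A claim of 90% implies a type II error of 10% in each group. The trial's hypothesis turns on premenopausal women responding more than postmenopausal women or men, so separate group results are likely to be read side by side. If the real type II error is 20% or more, a null result in postmenopausal women, for example, could be mistaken for well-powered evidence that amiloride does nothing there.

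**Working it through.** **Inputs (Protocol Section VI, Table 1).** Premenopausal women: δ = 1.0, SD of change = 1.2, calculated n = 30, final 34:17. Each other group: δ = 0.5, SD = 0.5, calculated n = 21, final 24:12. Alpha is 0.05.

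**Assumptions (not in the documents).** Two-sided test, the same SD in both arms, no placebo change, two-sample comparison of change from baseline.

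**1. Reproducing 30 and 21.** For an equally allocated two-sample comparison, n per arm = 2(1.96 + 1.2816)²(SD/δ)².
- Premenopausal: 2 × 10.507 × 1.44 = 30.26
- Others: 2 × 10.507 × 1 = 21.01

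Rounded to the nearest integer, these are Table 1's 30 and 21. Other formulas on the same inputs do not match: paired normal gives 15.1 and 10.5, paired t gives 18 and 13, one-sided two-sample gives 25 and 18. A paired test would give 30 and 21 only if 1.2 and 0.5 were single-visit SDs with zero correlation, but the table labels them SDs of the change. The two-sample origin is thus an inference, though it fits both rows.

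**2. Power at the listed sizes.** SE = SD × √(1/n₁ + 1/n₂). Normal power = Φ(δ/SE − 1.96). The t figures use the noncentral t with n₁ + n₂ − 2 degrees of freedom.
- 34:17: SE = 1.2 × √(1/34 + 1/17) = 0.356; δ/SE = 2.805; Φ(0.845) = 80.1%
- 24:12: SE = 0.5 × √(1/24 + 1/12) = 0.177; δ/SE = 2.828; Φ(0.868) = 80.7%

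**3. Implied attrition.** 1 − 30/34 = 11.8% and 1 − 21/24 = 12.5%. The same proportions leave 17 × 30/34 = 15 and 12 × 21/24 = 10.5 on placebo.

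| Amiloride:placebo | t | Normal |
|---|---|---|
| 30:30 (1:1 benchmark) | 88.8% | 89.8% |
| 21:21 (1:1 benchmark) | 88.5% | 90.0% |
| 34:17 as recruited | 78.5% | 80.1% |
| 24:12 as recruited | 78.5% | 80.7% |
| 30:15 after attrition | 73.1% | 75.0% |
| 21:10.5 after attrition | 72.5% | 75.4% |

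The benchmark rows show that most of the gap comes from the halved placebo arm; using t in place of normal accounts for 1 to 2 points. With 10 or 11 whole placebo completers instead of 10.5, the last row is 71.1% or 73.9% (t).

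**4. Sensitivity, as recruited (t unless stated; premenopausal women, then each other group).**
- Placebo also falls by 0.1 m/s: 69.7% and 59.4%
- Placebo rises by 0.1 m/s: 85.7% and 90.9%
- One-sided 0.05: 87% in both (88% normal)

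**5. Difference detectable with 90% power, as recruited.** Normal: 3.2415 × 0.356 = 1.16 and 3.2415 × 0.177 = 0.57 m/s. By t: 1.18 and 0.59 m/s.

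**6. The before-after reading.** Paired-t power on amiloride alone is 99.7% at n = 34 and at n = 24.

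**7. Pooled, for contrast.** The mean difference weighted by group size is (51 × 1.0 + 108 × 0.5)/159 = 0.66 m/s. With an SD of about 0.82, 106:53 has more than 99% power.

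**The case against.** The strongest reply is that the sentence speaks of each group's changes, under a table whose title and effect column describe baseline and treatment values on amiloride. Read literally, that is change from baseline, for which 99.7% exceeds 90%, so a promise of at least 90% is kept. That much stands. But this reading does not produce 30 or 21 from the labelled SD, 90% is not its power, and it leaves out the control arm of a placebo-controlled trial.

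A second reply is that a single change score is not the planned analysis. cfPWV is measured at baseline, week 12 and week 24, and the SAP fits a random-intercept model. If the effect is equal at both later visits and the two changes correlate 0.5, as that model implies with independent residuals, averaging them multiplies the variance by (1 + 0.5)/2 = 0.75. Power within a group is then about 89% (t) or 90% (normal) as recruited, and 84-86% after the implied attrition. This is the best case for the stated figure. It needs full retention and a contrast that neither document specifies.

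Two limits also stand. The result is sensitive to the placebo change: if placebo worsens by 0.1 m/s, the three smaller groups do reach 90%. And the attrition is back-calculated; the protocol does not call the step from 30 to 34 a dropout allowance, although about 12% is compatible with the past retention above 85% cited in Section X. The as-recruited figures of 79-81% do not depend on it.

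**Conclusion.** The concern holds. The stated 90% fits equal arms of 30 and 21, not the listed 34:17 and 24:12. For amiloride versus placebo within a group, with two-sided alpha 0.05, Table 1's effects and SDs, and no placebo change, the type II error is about 20-21% as recruited and 25-27% after implied attrition, against the 10% claimed. The figures concern a within-group comparison of change. They are not the power of the SAP's two-group mixed model, and a comparison pooled over all groups would be amply powered under the same inputs. The arithmetic is secure; which comparison the authors meant is inferred, because Section VI does not say.

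**What to change.** In Protocol Section VI:

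1. Name the comparison and test that Table 1 powers, with sidedness, assumed placebo change and any dropout allowance.
2. Delete the blanket statement that the final sizes give 90% power for each group. If before-after change on amiloride was meant, say so, and say that this is not the placebo-controlled comparison.
3. State the per-group amiloride-versus-placebo power under 2:1 allocation with its assumptions: about 79-81% as recruited and about 73-75% if the inflation in Table 1 is a dropout allowance. Give the differences detectable with 90% power: about 1.18 m/s in premenopausal women and 0.59 m/s in each other group.
4. Note that these figures do not describe the SAP's two-group mixed model.

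The cost is a change of wording and a table note. Recruitment, visits and analysis stay as they are; the stated power becomes less favourable.

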- Visit #1: Vital signs (blood pressure and heart rate), weight, DEXA, assessment of brachial and popliteal artery flow-mediated dilation (FMD), cfPWV, femoral artery blood flow, and oral glucose tolerance test (OGTT) (amount of blood drawn not exceeding 55 mL). OGTT will be done when glucose beverage is available. Entire visit is expected to take up to 6 hours. Women of childbearing age will undergo a pregnancy test prior to the DEXA scan and excluded if pregnancy is confirmed. Subject is dispensed the bottle of study drug/placebo and instructed how to take them.
- Visit #2 (1 week after starting the medication +6 days/-2 days): Vital signs, safety questionnaire for side effects, and blood draw for safety laboratories (basic metabolic panel). Entire visit is expected to take up to 30 minutes.
- Visit #3 (4 weeks after starting the medication +/- 6 days): Vital signs, safety questionnaire for side effects, and blood draw for safety laboratories (basic metabolic panel). Entire visit is expected to take up to 30 minutes.
- Visit #4 (8 weeks after starting the medication +/- 6 days): Vital signs, safety questionnaire for side effects, and blood draw for safety laboratories (basic metabolic panel). Entire visit is expected to take up to 30 minutes. If the prior safety visit labs have been within the protocol parameters this visit may be completed as a phone call visit to collect safety questionnaire for side effects and any changes in the subject's health.
- Visit #5 (12 weeks after starting the medication +/- 6 days): Vital signs, weight, DEXA, safety questionnaire for side effects, and blood draw for safety laboratories (basic metabolic panel) and general biochemistries. Subject also will have assessment of brachial and popliteal artery FMD and cfPWV. Women of childbearing age will undergo a pregnancy test prior to the DEXA scan and withdrawn from study if pregnancy is confirmed. Subject will be dispensed a new bottle of study drug/placebo. Entire visit is expected to take up to 3 hours.
- Visit #6 (16 weeks after starting the medication +/- 6 days): Vital signs, safety questionnaire for side effects, and blood draw for safety laboratories (basic metabolic panel). Entire visit is expected to take up to 30 minutes. If the prior safety visit labs have been within the protocol parameters this visit may be completed as a phone call visit to collect safety questionnaire for side effects and any changes in the subject's health.

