- Visit #7 (20 weeks after starting the medication +/- 6 days): Vital signs, safety questionnaire for side effects, and blood draw for safety laboratories (basic metabolic panel). Entire visit is expected to take up to 30 minutes. If the prior safety visit labs have been within the protocol parameters this visit may be completed as a phone call visit to collect safety questionnaire for side effects and any changes in the subject's health.

Visit #8 (24 weeks after starting the medication +/- 6 days): Vital signs (blood pressure and heart rate), weight, DEXA, waist circumference, safety questionnaire for side effects, and blood draw for safety laboratories (basic metabolic panel, lipid panel, and hemoglobin and hematocrit). Subject will also have assessment of brachial and popliteal artery FMD, cfPWV, femoral artery blood flow and oral glucose tolerance test (OGTT) (amount of blood drawn for safety labs, other biochemistries and OGTT not to exceed 70 mL). OGTT will be done when glucose beverage (75g) is available in a volume within 50ml of what was used in the baseline visit. These will minimize variability of the measurements related to changes in the volume of liquid ingested. Women of childbearing age will undergo a pregnancy test prior to the DEXA scan and withdrawn from study if pregnancy is confirmed. Entire visit is expected to take up to 6 hours.

Additional Safety Visits/unscheduled visits might be scheduled in cases of down titration of amiloride dose. Vital signs, safety questionnaire for side effects, and blood draw for safety labs (amount not to exceed 15mL). Unscheduled visits may also occur if safety lab specimens are compromised for any reason or questionable accuracy of the result. Safety labs will then be repeated (amount of blood drawn not to exceed 15 mL).

Medication changes and adverse events collected through out subjects' participation.

Special considerations in case of unforeseeable hardships such as public health emergencies or weather-related events.

In the event of subjects not being able to complete study visits for the reasons described above the following remedial steps will be taken:

- Visits #3,4, 6 and 7 can be completed via a phone interview during which the subject will answer the safety questionnaire (no changes in compensation).

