- In case that subject cannot complete safety visit #2, every effort will be made to complete this visit within 7 days of the original scheduled date. In case that the visit cannot be completed, the subject will be instructed to discontinue study medication and his/her participation in the study will be completed. Safety officer will be informed.
- In case that study visit #5 cannot be completed and providing patient has completed at least 2 in person visits since the medication was started, study medication will be mailed by investigational pharmacy for subject to continue treatment. Safety officer will be informed. Compensation will be unchanged.

In the event of the Clinical Translational Science Unit (CTSU) not being available or if it is considered by the study physician that performing studies there can increase risk of exposure to infectious agents or related hazards, the following alternative sites will be made available for screening, safety and study visits.

- MU Physical Activity and Wellness (PAW)
- University hospital clinic rooms

These locations are not carpeted, and we do not anticipate an increased risk for the subjects given that medical supervision and nursing staff assistance will be unchanged.

Detail on procedures:

DEXA scan: to assess body composition with dual-energy X-ray absorptiometry.

Oral glucose tolerance test: After an overnight fast, a catheter will be inserted into an antecubital vein for sampling of venous blood. Additional blood will be collected every 15-30 mins over the next 120 mins after consuming the glucose beverage (75 grams of dextrose).

Arterial Stiffness and Blood Pressure: The SphygmoCor XCEL device will be used to assess blood pressure and aortic pulse wave velocity, a marker of arterial stiffness. A blood pressure cuff will be wrapped around the upper arm and upper leg. They will periodically inflate to ~200 mmHg for less than 60 seconds. A pressure sensor (tonometer) will be placed over the skin of the neck region to obtain the pressure wave form in the carotid artery. This measure will be performed in duplicate.

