Oral Glucose Tolerance Test (OGTT): This procedure could cause possible nausea from glucose beverage. **DEXA and anthropometrics:** Radiation exposure during DEXA is equivalent to about two percent of the average radiation dose from all sources (natural background radiation, consumer appliances, radon gas, medical tests, etc.) that a person in the United States receives each year. Subjects who have participated in any other research study or medical procedure involving significant ionizing radiation exposure (e.g., multiple chest x-rays) in the past 12 months will be excluded. For female subjects, a urine pregnancy test is administered before the DEXA. Body weight is measured to the nearest 0.1 kg and height to the nearest 0.1 cm.

Amiloride therapy: In previous clinical trials with higher doses (10 mg) amiloride was well tolerated. Nevertheless, our team of investigators is well aware of the potential side effects (1-10%): dizziness, fatigue headache, hyperkalemia. Subjects will be closely monitored during the drug/placebo treatment intervention. After each safety visit, [name] and [name] will review blood pressure and heart rate readings, as well as results of renal function and electrolyte levels. The treatment will be discontinued in case of hyperkalemia > 5.5 mEq/L, creatinine increases more than 30% above baseline, hypotension or severe dizziness. If the subject exhibits hyperkalemia or if creatinine increases more than 30% above baseline, the study team will repeat safety labs until they return to baseline. If a subject exhibits potassium > 5.5 mEq/L, creatinine increases more than 30% above baseline, hypotension or severe dizziness on the 5 mg dose, medication will be held for 1 week and a lower dose of amiloride will be started (half of a 5mg tablet). Once the dose of half of a 5mg tablet has been started, a safety visit will be completed 1 week later. If no clinically significant abnormalities are documented, safety visits will proceed as scheduled for the 5 mg dose. If there are clinically significant abnormalities

documented after down titration of amiloride, subjects will discontinue medication and participation in the clinical trial is terminated. In the event of a severe unexpected adverse event the subject will be unblinded to facilitate medical care.

Placebo: Pill Capsule: There is a potential risk for an allergic reaction to the gelatin capsule.

Placebo: Cellulose: These are no known risks.

Protection Against Risks

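### Minor safety gap: when Visit 5 is missed through hardship, study drug can be mailed with nothing to replace the pregnancy test lost with that visit

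*Protocol*

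**What the plan says.** The rule sits in Protocol section VII, in the part headed "Special considerations in case of unforeseeable hardships such as public health emergencies or weather-related events". For a Visit 5 that cannot be completed it says that "study medication will be mailed by investigational pharmacy for subject to continue treatment", "providing patient has completed at least 2 in person visits since the medication was started". The safety officer is told and the subject's payment is kept. No pregnancy test, and no other substitute for the missed assessments, is attached to the mailing.

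Pregnancy tests appear at three visits in the section VII schedule:

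- Visit 1 (baseline): "Women of childbearing age will undergo a pregnancy test prior to the DEXA scan and excluded if pregnancy is confirmed".
- Visit 5 (week 12): "Women of childbearing age will undergo a pregnancy test prior to the DEXA scan and withdrawn from study if pregnancy is confirmed". The new bottle of study drug or placebo is handed out at this same visit.
- Visit 8 (week 24): the same sentence as at Visit 5.

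Section VIII also ties the test to the scan: "For female subjects, a urine pregnancy test is administered before the DEXA".

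No other visit lists a pregnancy test. Visits 2, 3, 4, 6 and 7 consist of vital signs, a side-effect questionnaire and a basic metabolic panel. Unscheduled visits are similar: "Vital signs, safety questionnaire for side effects, and blood draw for safety labs (amount not to exceed 15mL". Under hardship, "Visits #3,4, 6 and 7 can be completed via a phone interview during which the subject will answer the safety questionnaire".

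**The concern.** At a completed Visit 5, the pregnancy test, the withdrawal rule and the hand-over of the next bottle all fall in one visit. The hardship route keeps the bottle and drops the test. Visit 1 comes before dosing and Visit 8 at the end of it, so Visit 5 is the only scheduled test that can stop dosing partway through. A woman whom that test would have withdrawn could instead be sent about 12 more weeks of study drug, with her next planned test when treatment is over.

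The stake is participant safety, measured against the protocol's own rule that a confirmed pregnancy ends participation. Nothing in the efficacy analysis depends on it.

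**Working it through.** **1. Can any qualifying visit stand in for the test?** The two in-person visits that permit mailing must fall between drug start and Visit 5, so they are Visits 2, 3 and 4 or unscheduled safety visits. None lists a pregnancy test. After the mailing come Visits 6 and 7, which list none either and may be phone interviews under hardship. The next planned test is at Visit 8.

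**2. Test spacing.** Take the day of Visit 1, when drug is dispensed, as day 0 (an assumption). Visits 5 and 8 each carry a window of 6 days either way.

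- Visit 5: 12 × 7 = 84, so day 78 to 90.
- Visit 8: 24 × 7 = 168, so day 162 to 174.
- Visit 1 to Visit 5: 78 to 90 days.
- Visit 5 to Visit 8: 162 − 90 = 72 to 174 − 78 = 96 days.
- Longest routine interval: max(90, 96) = 96 days.
- Mailed route, Visit 1 to Visit 8: 162 to 174 days.

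The further exposure of a woman already pregnant at Visit 5 is the Visit 5 to Visit 8 interval, 72 to 96 days, if she takes the mailed supply until Visit 8.

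**3. Reach.** Table 1 in section VI targets 34 premenopausal women on amiloride and 17 on placebo: 34 + 17 = 51, and 51/159 = 32% of all subjects. This takes the premenopausal group as the women concerned. Only hardship cases among them are affected.

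**4. Expected number of pregnancies.** The documents give neither a mailing rate nor a conception rate. I assume that 2% to 15% of these women are mailed a bottle, and that 1% to 10% conceive per year on contraception.

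| Quantity | Low | High |
|---|---|---|
| Women mailed drug | 51 × 0.02 = 1.02 | 51 × 0.15 = 7.65 |
| Probability of conception, Visit 1 to Visit 5 | 1 − 0.99^(78/365) = 0.00215 | 1 − 0.90^(90/365) = 0.02564 |
| Pregnancies untested until Visit 8 | 1.02 × 0.00215 = 0.002 | 7.65 × 0.02564 = 0.196 |
| Of these, on amiloride (two-thirds) | 0.68 × 0.00215 = 0.0015 | 5.1 × 0.02564 = 0.131 |
| Ceiling, all 51 mailed drug | 51 × 0.00215 = 0.11 | 51 × 0.02564 = 1.31 |

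For given assumed rates these figures err on the high side, because a very recent conception would not show at Visit 5. Conceptions after week 12 are not counted, since the Visit 5 test would not have found them.

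**The case against.** The strongest reply is that the test is a scan safeguard. Every mention ties it to DEXA, and with no scan its radiation purpose falls away. The same withdrawal sentence appears at Visit 8, where no more drug is dispensed, so it may never have been meant to control drug supply. The documents state no fetal risk of amiloride, and section II describes an FDA-approved dose in a population not expected to be at higher risk. This stands as a limit on importance, but it does not remove the gap. Pregnancy is an exclusion in section V, and the consequence of a positive Visit 5 test is leaving the study, not skipping the scan. As written, the mailed route has no scheduled check on that rule until treatment ends.

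The existing safeguards are also real. Women not using contraceptives or planning pregnancy are excluded, adverse events are collected throughout, and routine phone versions of Visits 4, 6 and 7 ask about changes in health. Alternative sites are provided, and nothing bars a late Visit 5 or an unscheduled test. These lower the risk. However, the eligibility criteria apply at entry, a phone call can find only a pregnancy the woman already suspects, and no text requires a late visit or test. The 162 to 174 days therefore describe the plan followed to the letter.

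Two further points stand. The figure of 51 is not a strict bound, because childbearing age is undefined and section VI classes women as postmenopausal after only 6 months without menses. The same rule also drops the week-12 metabolic panel without a substitute. That is a separate and arguably more important gap, because hyperkalemia is a named drug risk, and a urine kit would not close it.

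**Conclusion.** The gap is real and minor. Followed as written, the mailing rule can supply about 12 more weeks of study drug without the one mid-treatment pregnancy test the protocol schedules. The lengthened interval measures test spacing, not demonstrated added risk. Under the assumed rates, about 1 to 8 women would be mailed drug and well under one pregnancy would go untested until Visit 8, with a ceiling of 0.1 to 1.3 if every premenopausal woman were mailed a bottle. The spacing figures rest on dosing from the day of Visit 1, no make-up of Visit 5 and no unscheduled test. The counts also rest on taking the 51 premenopausal women as those affected. The point rests on the protocol's own withdrawal rule and not on any claim about amiloride in pregnancy. Sample size, power and the primary analysis are untouched.

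**What to change.** In the hardship provisions of section VII, add one sentence: before study medication is mailed to a woman of childbearing age, she must have a negative urine pregnancy test, for example from a home kit with the result confirmed by phone. The cost is one sentence in an amendment, plus one kit and one call per mailed bottle, replacing a test already planned at the missed visit. Supply could be delayed by a few days.

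The SAP is dated November 2025 and written in the past tense, so dosing may already have ended. In that case no amendment is needed: check pharmacy records for bottles mailed to such women without a test. Neither action changes the sample size or the analysis.
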